3.4 Exploratory Endpoints

3.4.1 Clinical Endpoints

The following will be evaluated in Stage 2 and Stage 3:

- Proportions of participants in each arm who achieve responder status as assessed by SRI-4, SRI-6, and SRI-7 (as defined in Section 3.5.2, *Systemic Lupus Erythematosus Responder Index*) every 4 weeks through Week 24.
- Incidence rates for Mild/Moderate and Severe flares accumulated during the treatment period. Three flare assessments will be evaluated independently:
 - a. Thanou modified SELENA-SLEDAI Flare Index (see Section 19.3.5, *Thanou Modified SFI*)[2].
 - b. BILAG flare, defined as a new A or 2 new Bs.
 - c. BILAG flare, defined as any item marked new or worse that could support a BILAG A (severe flare) or 2 organs with items marked new or worse that could support a BILAG B (moderate flare).
- Incidence rates for Mild, Moderate and Severe disease activity. Assessments across multiple organ/systems are rated using:
 - a. LFA-REAL clinician assessment
 - b. LFA-REAL participant assessment

- Longitudinal profiles of the Physical Component Summary, Mental Component Summary, and individual domains of the SF-36 patient-reported outcome (PRO) that are observed over the treatment period.

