2.3 Secondary Objectives

- To describe the effects of long-acting corticosteroid injections, MMF, MMF plus voclosporin, and placebo on measures of safety and toxicity.
- To describe the effects of MMF, MMF plus voclosporin, and placebo on exploratory clinical response measures and disease flare indices.
- To describe the effects of MMF, MMF plus voclosporin, and placebo on patient-reported quality of life indices.

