8.2.4.4 LFA REAL

The LFA-REAL Clinical Reported Outcome (ClinRO) and PRO provide an integrated system that can directly compare a patient's and clinician's view on individual items that are part of active lupus disease [82, 83]. For both the patient and clinician components, the instrument is constructed as a series of individual anchored visual analogue scales with the ability to assess disease by symptom, by organ or by global total disease. All scales default to 0, so it is easy and quick to choose the limited number of symptoms likely to be present at a given time and score their severity.

The patient's component is complementary but not identical to the clinician's component [84, 85]. Unlike the other PROs to be used in this trial, this is a disease activity assessment by the patients, specific to SLE signs and symptoms and it is not a quality of life assessment. Thus, the information it might provide is not redundant to, but might be complementary to other PRO measures.

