13.4.6 Analyses of Exploratory Endpoints

Details of the exploratory analysis of clinical endpoints will be outlined in the SAP. For mechanistic endpoints, exploratory analyses will be conducted separately for subgroups allocated to each Stage 2 treatment arm because participants entering Stage 3 from the different treatment arms are not comparable at the point of re-randomization. Mechanistic plans are to explore baseline (pre-re-randomization) gene expression and protein level patterns among those who respond (or do not respond) to MMF and MMF plus voclosporin, and to describe differences between the 2 arms. Response will be defined using BICLA at 24 weeks post re-randomization.

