13.7 Sample Size Considerations

The goal of Stage 2 of the study is to evaluate the potential effectiveness of MMF within previously-identified immunologically-homogeneous clusters of lupus patients. To place these cluster comparisons in the context of a successful trial, target enrollment is based on power to show superiority of MMF over placebo in a pooled lupus population.

In previous studies using BOLD designs in lupus populations [22, 93, 94] where long-acting corticosteroids were administered during the treatment withdrawal stage, survival free-from-failure at 6 months in untreated or placebo-treated participants ranged from 5-20% [25]. These studies included participants with a range of disease activity, had differing rules on implementation of background steroids and different definitions for treatment failure. By limiting steroids and carefully adhering to entry criteria to recruit an appropriate population with active lupus disease activity, and by defining treatment failure to include individuals who receive rescue medications post-randomization or who withdraw from treatment prematurely, a placebo survival at 24 weeks of 15% or less should be achievable. In the MMF arm, a minimum clinically meaningful improvement would be 35% survival at 24 weeks.

A study design with 120 participants randomized 1:1 to placebo or MMF will have between 74% to \geq 95% power if placebo survival at Stage 2 Week 24 ranges from 15% to 10% and MMF survival at Stage 2 Week 24 ranges from 35% to 50% (2-sided, $\alpha=0.05$); power is \geq 80% when MMF survival at Stage 2 Week 24 is at least 37%. Power for a two-sample landmark analysis was computed for a Z-Test with unpooled variance using binomial enumeration.

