19.3.6 LFA-REAL CLINRO

LFA-REAL™ (RAPID EVALUATION OF ACTIVITY IN LUPUS)
[CLINICIAN REPORT]

DIRECTIONS: Thinking of the past month, put one line () anywhere through each scale below to assess the severity of lupus activity in each symptom/organ for the patient. Score only lupus disease activity (not chronic damage). If there is no activity in a particular symptom/organ, mark 0 (none) for that organ/system. Rate each active symptom/organ separately. Use "other" scales for symptoms/organs not listed here. The sum of organ scores provides the global disease activity. When performing monthly assessments, look back at your last form and place your mark considering the patient's progress during the past month.

Examples:

A moderate arthritis, not quite severe might be rated like this:  A mild arthritis, getting better this month might look like this: 

How severe was each organ/system disease activity over the past month?**MUCOCUTANEOUS - GLOBAL**

Symptom score _____ mm

Mucocutaneous components:

[figure not shown]
mm

mm

mm

MUSCULOSKELETAL - GLOBAL

[figure not shown]
[figure not shown]
[figure not shown]
[figure not shown]
mm

Musculoskeletal components:

[figure not shown]
[figure not shown]
[figure not shown]
mm

mm

How severe was each organ/system disease activity over the past month?**CARDIORESPIRATORY** (please specify symptom) _____**NEUROPSYCHIATRIC** (please specify symptom) _____**RENAL** (give one score for nephritis, may specify CLASS if known) _____**HEMATOLOGIC** (please specify symptom) _____**CONSTITUTIONAL** (please specify symptom) _____**VASCULITIS** (please specify symptom) _____

Optional, additional scales may be used to rate multiple features within one of the specified organs or to rate features in more rarely involved organs (e.g. GI, ophthalmic, etc.)

OTHER (Use for additional features, please specify organ and symptom): _____**OTHER (Use for additional features, please specify organ and symptom):** _____**OTHER (Use for additional features, please specify organ and symptom):** _____**Total Score****mm***(Right column only)*

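### LFA-REAL is scored in millimetres, but its only endpoint counts mild, moderate and severe activity, so change within a band is lost

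*Combined protocol and SAP*

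**What the plan says.** Section 8.2.4.4 describes the measurement, for both the patient and the clinician parts: "the instrument is constructed as a series of individual anchored visual analogue scales with the ability to assess disease by symptom, by organ" or overall. The clinician form in Section 19.3.6 adds that "The sum of organ scores provides the global disease activity". Both forms (Sections 19.3.6 and 19.3.7) have mm fields and a total score. Tables 8.1 and 8.2 schedule both forms at every Stage 2 visit and from Week 4 in Stage 3.

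Section 3.4.1 then lists the endpoint, for both stages: "Incidence rates for Mild, Moderate and Severe disease activity. Assessments across multiple organ/systems are rated using" the clinician and the patient form. The synopsis says the same. The mm score is not named as an endpoint in either place. The next item in the same list keeps the SF-36 summary and domain scores as profiles over the treatment period.

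On analysis, Section 13.4.6 says: "Details of the exploratory analysis of clinical endpoints will be outlined in the SAP". The related objective in Section 2.3 is descriptive: "To describe the effects of MMF, MMF plus voclosporin, and placebo on exploratory clinical response measures and disease flare indices".

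**The concern.** A graded score is collected every four weeks and then reduced to three bands. A participant who moves from the top to the bottom of the moderate band counts as unchanged, while a small move across a boundary counts as a full step. Hypothesis 1 (Section 2.1.1) is that steroid-induced improvement is lost faster on placebo, which is a question about level over time. A score followed by visit answers it directly.

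Section 13.4.6 defers the analysis to the SAP but does not defer the endpoint definition. A SAP that follows Section 3.4.1 as written would summarise the bands and omit the score. What is at stake is the information that an exploratory measure, with matching clinician and patient versions, can give about MMF and voclosporin. The primary comparison is not affected.

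**Working it through.** **The plan's own power figure.** Section 13.7 states power for the primary endpoint only: "A study design with 120 participants randomized 1:1 to placebo or MMF will have between 74% to" at least 95% when "placebo survival at Stage 2 Week 24 ranges from 15% to 10% and MMF survival at Stage 2 Week 24 ranges from 35% to 50"%. Exact enumeration of the unpooled Z-test with 60 per arm gives 73.8% at 15% against 35% (stated 74%) and 80.7% at 15% against 37% (stated at least 80%). The figures reproduce. They concern treatment failure and say nothing about LFA-REAL.

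**Inputs for LFA-REAL.** From the documents: 120 randomized 1:1, so 60 per arm in Stage 2; about 18 + 24 = 42 per arm in Stage 3 (Section 13.7). Assumed, because the documents give nothing: a normal score at one visit, lower on MMF by d = 0.4, 0.5 or 0.6 SD, two-sided 0.05.

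**Score analysed as it is.** Two-sample t-test with noncentrality d × √(n/2). At d = 0.5 this is 0.5 × √30 = 2.74.

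**Score cut once.** If a share q of placebo lies above the cut, the MMF share is 1 − Φ(z + d) with z = Φ⁻¹(1 − q). At d = 0.5, q = 50% becomes 1 − Φ(0.5) = 30.9%, and q = 20% becomes 1 − Φ(0.842 + 0.5) = 9.0%. Power is by exact enumeration of the pooled Z-test.

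| Analysis, 60 per arm | 0.4 SD | 0.5 SD | 0.6 SD |
|---|---|---|---|
| Score | 58.4% | 77.5% | 90.3% |
| Cut, 50% of placebo above | 41.6% | 57.9% | 72.8% |
| Cut, 30% above | 35.7% | 49.7% | 63.3% |
| Cut, 20% above | 28.2% | 39.7% | 51.6% |
| Cut, 10% above | 19.7% | 26.5% | 33.8% |

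The smallest loss is 58.4 − 41.6 = 16.8 points and the largest is 90.3 − 33.8 = 56.5 points, hence about 17 to 57. With 42 per arm and 0.5 SD, the score has 62% power, against 46% (50% cut) or 31% (20% cut).

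**Bands kept in order.** The endpoint names three levels, so a single cut is not the only reading. The check here is a tie-corrected rank test on three or four ordered levels, by normal approximation, with d set so that the score has 70%, 80% or 90% power. It loses about 7 to 13 points over a range of band shares. Simulating three levels at 0.5 SD gives a loss of about 10 points with equal thirds in the placebo arm, 15 with a 50/30/20 split, and 21 to 23 with 60/30/10. The overall range is about 7 to 23 points, larger when the top band is small.

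**Adjusting the score for its baseline.** With an assumed correlation of 0.5, the effective shift is d/√(1 − 0.25). Power at 60 per arm rises to 70.9%, 88.0% and 96.4%, a gain of about 6 to 13 points over the unadjusted score.

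**The case against.** **No test is planned.** The endpoint is exploratory, the objective is to describe, and the methods are left to the SAP. Strictly, there is no planned power to lose. This stands. The percentages measure how much information the bands discard, and they are not a shortfall in the trial's design power.

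**Incidence may suit the design.** A reader might infer that incidence is the wrong idea because everyone enters with active disease. The documents do not support that. Section 4.2.2 requires the physician to rate the participant moderately or much better after the steroid injections, and the participant to agree, before randomization. Return of moderate or severe activity after that improvement is a sensible thing to count. This argues for keeping the bands as a summary, but not for dropping the score.

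**The bands may be defined on the forms.** The forms use the words mild, moderate and severe, and the scale figures are not shown in the text supplied. Missing cut-points therefore cannot be held against the plan.

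**The score comparator is optimistic.** Under Section 13.7, 15% and 35% failure-free at Week 24 leave 0.15 × 60 = 9 and 0.35 × 60 = 21 participants who have not failed. A t-test on 9 against 21 has only 16%, 23% and 31% power at 0.4, 0.5 and 0.6 SD. This rules out a Week 24 completers' comparison. It does not rule out a repeated-measures analysis that uses earlier visits and the failure visit. In a simulation with failure driven by the score (about 79% of placebo and 62% to 69% of MMF failing, all settings assumed), a baseline-adjusted mixed model with the failure-visit score kept its 5% error rate. It also had clearly more power than counting participants ever above a cut.

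**Normality is unsupported.** Section 8.2.4.4 says the scales default to zero and few symptoms are likely at a time, and the clinician form allows optional extra scales. The total may well be skewed. This stands as a limit on the figures.

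**Conclusion.** The point holds as a low-impact improvement. The mm score is collected on both forms and enters no listed endpoint, while a comparable patient-reported score in the same list is kept as a score. Reducing it to bands discards information. How much is conditional on a normal score, 60 per arm and 0.4 to 0.6 SD: about 17 to 57 points of power for one yes/no cut, and about 7 to 23 points if the bands are analysed in order.

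A reader might infer that the plan itself loses some fixed amount of power. The documents do not support this: they give no LFA-REAL SD, effect, band shares or test, and they name three levels, not one cut. Nor is this the trial's only graded activity measure; the PGA and the hybrid SLEDAI are collected on the same schedule.

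**What to change.** In Section 3.4.1 and the synopsis, name the LFA-REAL total score in mm, for each form separately, at each visit through Week 24 of the stage, as the endpoint.

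In the SAP, analyse it with a repeated-measures mixed model containing:
- arm, visit and arm-by-visit;
- the randomization stratum for that stage (gene expression group in Stage 2; Stage 2 assignment and injection at failure in Stage 3);
- the stage-baseline score (Day 0 in Stage 2; the last assessment before re-randomization in Stage 3).

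Include the score from the failure visit, so that departure after failure depends on a value already in the model. State how the optional scales on the clinician form enter the total. Keep the mild, moderate and severe bands as a descriptive table, giving the cut-points, the scale used and the handling of repeated visits.

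The cost is endpoint and SAP wording and one standard model per form, with no added visits or assessments. The drawback is that estimates at later visits rest on a missing-at-random assumption after failure, which should be stated with the results.

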3.4.2 Mechanistic Endpoints

The following pharmacodynamic markers will be evaluated in Stage 2 and Stage 3:

- Differential expression, at the module or single gene level, between participants within immunologically-homogenous clusters who do and do not obtain a clinical response.
- Identification of complex immunophenotypes characterizing clinical response or non-response to study treatment.
- Longitudinal profiles of TWEAK, CR3, FYN, IL16, IL17RA, and IL2RB over 24-week treatment periods.

3.5 Definitions

3.5.1 Treatment Failure

Treatment failure is defined as the first occurrence after randomization (Stage 2) or as the first occurrence after re-randomization (Stage 3) of any of the following events:

- Corticosteroid injections or treatment with a new or increased lupus medication, except the occasional use of corticosteroids for reasons not associated with SLE flare (see Section 7.1.2.2, *Prednisone (or equivalent)* for additional information); or
- BILAG flare, defined as any item marked new or worse that could support a BILAG A (severe flare) or 2 organs with items marked new or worse that could support a BILAG B (moderate flare), and if the participant's condition is deemed by the investigator to be "moderately worse" or "much worse" compared to the day of randomization, as assessed by the CGI-C; or
- Premature permanent discontinuation of study-assigned treatment for any reason.

For Stage 2, the reference values for the CGI-C should be the investigator's determination of the participant's condition at the Stage 2 Day 0 Randomization Visit. For Stage 3, the reference values for the CGI-C should be the investigator's determination of the participant's condition at the most recent assessment before the Stage 3 Re-randomization Visit.

3.5.2 Systemic Lupus Erythematosus Responder Index (SRI)

A response for the SRI-4, SRI-6 and SRI-7 is defined as meeting the following four criteria at the time of the SRI assessment:

- For SRI-4, SRI-6, and SRI-7, a decrease in the Hybrid Systemic Lupus Erythematosus Disease Activity Index (H-SLEDAI) total score of ≥ 4 , 6, or 7 points from the reference visit.
- No new BILAG A scores among organs scored as B, C, D, or E at the reference visit, and
- ≤ 1 new BILAG B scores among organs scored as C, D, or E at the reference visit, and
- No worsening (≤ 0.3 point increase) in Physician Global Assessment (PGA) compared to the reference visit.

For Stage 2 and Stage 3, the reference value for SRI-4, SRI-6, and SRI-7 will be the H-SLEDAI total score, BILAG scores, and PGA obtained at the Screening Visit. For Stage 3, additional supportive analyses will use the most recent assessment before the Stage 3 Re-Randomization Visit as the reference value for the H-SLEDAI total score, BILAG scores, and PGA.

3.5.3 BILAG-based Combined Lupus Assessment (BICLA)

Clinical response at Week 24, defined by the BICLA [71] as follows:

- All BILAG A scores must improve to B, C, or D, and
- All BILAG B scores must improve to C or D, and
- No new BILAG A scores among organs scored as B, C, D, or E, and
- ≤ 1 new BILAG B scores among organs scored as C, D, or E, and
- No worsening of H-SLEDAI total score, and
- Less than a 10% increase (worsening) in the Physician's Global Assessment (visual analogue scale).

For Stage 2 and Stage 3, the reference values for BILAG, H-SLEDAI total score and PGA are the assessments obtained at the Screening Visit. For Stage 3, additional supportive analyses will use the most recent assessment before the Stage 3 Re-Randomization Visit as the reference value for H-SLEDAI total score, BILAG scores, and PGA.

3.6 Stratification, Randomization, and Blinding

For Stage 2 randomization, participants will be stratified by screening gene expression signature:

- Group 1: high interferon and high inflammation
- Group 2: low inflammation and high B Cells (interferon can be high or low)
- Group 3: other profiles not included in groups 1 or 2
- Group 4: gene expression signature results unavailable (e.g. due to shipping or laboratory error)

For Stage 3 re-randomization, participants will be stratified by the Stage 2 treatment assignment: MMF vs Placebo MMF along with whether or not a long-acting corticosteroid injection was given at the time of Stage 2 treatment failure.

The randomization will be performed by the Division of Allergy, Immunology, and Transplantation (DAIT) Statistical and Clinical Coordinating Center (SCCC). Blinding will be maintained for all study participants and trial personnel throughout the study, except for the study site pharmacist. Treatment assignments will be centrally randomized and communicated to the unblinded study site pharmacist. The investigators, clinic personnel, and participants will not be informed regarding the intervention assignment until the study is unblinded. Laboratories performing assays for this protocol will be blinded to the identity and group assignment of biological materials to be studied.

3.6.1 Procedure for Unblinding

Unblinding must be approved by the study NIAID Medical Monitor unless an immediate life-threatening condition has developed and the Medical Monitor is not accessible. The site investigator will notify the NIAID Medical Monitor, Protocol Chair and the SCCC of the unblinding event on the next business day. The emergency unblinding will also be reported to the DSMB by the NIAID Medical Monitor.

A full account of the event will be recorded, including the date and time of the unblinding, the reason for the decision to unblind, and the name of the individual who made the decision and the names of the Medical Monitor and others who were notified. The reasons for unblinding of a participant's treatment will be included in the final study report.

Unblinding the study due to an approved interim analysis, final analysis, or study termination will require written approval from NIAID.

4 Selection of Participants

4.1 Rationale for Study Population

SLE affects all races, all genders, and all ages, but is more prevalent in women in their childbearing years who are of African, Asian or Native American Ancestry. This will be a trial of individuals between the ages of 18 and 60 with no restrictions for race or gender. These criteria are inclusive of most people with SLE, with restrictions for those who are medically vulnerable or who cannot complete all of the procedures. Children are not included since they usually have more severe disease, and this is unlikely to be a safe protocol for them. The current treatments for SLE are inadequate to prevent recurrent flares, progressive disability, and early mortality, often from accelerated atherosclerosis or infection. The population of SLE patients selected for this trial is an underserved community with chronic, sometimes life-long symptoms that significantly affect their work productivity, family relationships and overall quality of life. However, flares tend to be moderate in severity and primarily affect the musculoskeletal and mucocutaneous systems, without life-threatening or organ-threatening components. Our qualification criteria, adjudication process, and pre-testing for early flare markers have all evolved from our past experience with (and test development from) the BOLD study [22].

The BOLD study was conducted safely [22] ([clinicaltrials.gov # NCT00987831](https://clinicaltrials.gov/ct2/show/NCT00987831)), as was our past pilot study of MMF [NCT00594932](https://clinicaltrials.gov/ct2/show/NCT00594932), which used a BOLD design, and since then two industry-sponsored trials have utilized the same design - [NCT00774943](https://clinicaltrials.gov/ct2/show/NCT00774943), [NCT02725515](https://clinicaltrials.gov/ct2/show/NCT02725515) - one of which is completed and recently published[23]. We are also in the process of completing three Investigator-initiated trials in Oklahoma using the BOLD design: [NCT02270957](https://clinicaltrials.gov/ct2/show/NCT02270957), [NCT03355482](https://clinicaltrials.gov/ct2/show/NCT03355482), [NCT02270970](https://clinicaltrials.gov/ct2/show/NCT02270970). All of the unpublished SLE trials using the BOLD design are a short time from completion and there has been no unacceptable safety signal to date. However, selection of the appropriate participant population for a trial of this structure is critical, both to its success in obtaining interpretable results and for participant well-being and safety. Our Inclusion and Exclusion Criteria address the selection and verification of this very population.

